7.2.3. Prohibited Medications

Patients are not allowed to receive other anticancer therapy, including surgery, RT (other than protocol-specified), and cytotoxic, biologic, or hormone therapy. Hormone replacement therapy is allowed.

Therapeutic anticoagulation with heparin, warfarin, or other anticoagulants is not allowed, with the exception of low molecular weight heparin for the treatment of patients with thromboembolic events.

Low-dose aspirin, non-steroidal anti-inflammatory agents and thrombolytics to establish patency of indwelling venous catheters are allowed, as is prophylactic anticoagulation for venous access devices as long as INR is ≤ 1.5 and aPTT $\leq 1.5 \times$ institutional ULN ([Section 5.1](#)).

The primary metabolic pathway for pamiparib involves the CYP3A isoform. The concurrent administration of compounds/substances presented in [Appendix 6](#) are prohibited, as they are associated with possible interactions with pamiparib through the CYP3A metabolic pathway, as well as other various metabolic interactions.

7.2.4. Medications to Be Used with Caution

The primary metabolic pathway for pamiparib involves the CYP3A isoform. Concurrent administration of strong/moderate inhibitors of CYP3A or strong CYP3A inducers is not allowed. Pamiparib is an inhibitor of CYP2C9; careful monitoring should be used when co-prescribing CYP2C9 substrates with a narrow therapeutic index, such as phenytoin and warfarin. Examples of these medications are listed in [Appendix 7](#), and these should be used cautiously with drug concentration monitoring where appropriate.

In addition to CYP3A, pamiparib can also be metabolized by CYP2C8 in human liver microsomes, but to a lesser extent. See [Appendix 7](#) for medications that should be used with caution for that reason.

8. STUDY ASSESSMENTS

8.1. Study Flow and Visit Schedule

The study-specific assessments and procedures with allowed time windows for Arm A, Arm B, and Arm C, and maintenance treatment for Arms A and B are outlined in [Appendix Table 1](#), [Appendix Table 2](#), [Appendix Table 3](#), and [Appendix Table 4](#), respectively. Assessment of safety of the combination therapies will be based on AE monitoring and reporting (including attribution of AEs and serious adverse events [SAEs]), clinical laboratory testing, vital signs, ECGs, physical examinations, and PK assessments as outlined in [Sections 8.2](#), [8.4](#), and [8.5](#), as well as [Appendix 1](#). Assessments of efficacy will occur as outlined in [Section 8.3](#) and [Appendix 1](#).

8.2. Patient Demographics and Other Baseline Characteristics

8.2.1. Demographics

Demographic data will include gender, date of birth (or age), and race/ethnicity.

8.2.2. Medical History

Clinically significant medical history findings (eg, previous diagnoses, diseases or surgeries) started before signing the informed consent, and considered relevant for the patient's study eligibility will be collected and captured, including baseline severity, if ongoing, in the eCRF. Clinically significant is defined as any events, diagnoses or laboratory values that require treatment or follow-up, or the presence of signs or symptoms that require medical intervention. Concurrent medical signs and symptoms must be documented to establish baseline severities.

For the GBM history, the date of initial diagnosis and current disease status, staging, sites of disease, prior anticancer therapies, dates administered, responses and duration of response to these treatments will also be recorded.

8.2.3. Other Baseline Characteristics

Information will also be collected regarding prior medications/significant non-drug therapies, childbearing potential ([Appendix 4](#)) and any other assessments that are done for the purpose of eligibility for inclusion into the study. For further details on eligibility assessments, please see [Section 5](#) and [Appendix 1](#).

8.3. Tumor Assessments

8.3.1. Magnetic Resonance Imaging (MRI)

Tumor assessments will include all known or suspected disease sites. The minimum recommended MRI sequences include: (i) parameter-matched precontrast and post-contrast inversion recovery-prepared, isotropic 3D T1-weighted gradient-recalled echo; (ii) axial 2D T2-weighted turbo spin-echo acquired after contrast injection and before post-contrast 3D T1-weighted images to control timing of images after contrast administration; (iii) precontrast, axial 2D T2-weighted

fluid-attenuated inversion recovery; and (iv) precontrast, axial 2D, 3-directional diffusion-weighted images. MRIs will be performed at screening (within 14 days of Day 1) and every 8 weeks (± 7 days), unless otherwise specified in [Appendix 1](#).

Non-contrast cranial MRI may only be used to document disease in those patients who are allergic to contrast. Tumor assessments should be repeated at the end of treatment visit if more than 4 weeks have passed since the last evaluation.

The same imaging technique used at screening should be used throughout the study.

Anti-tumor activity will be assessed through radiologic tumor assessments conducted at screening, during treatment as specified in the Schedule of Activity, whenever disease progression is suspected (eg, symptomatic deterioration), and at the time of withdrawal from treatment (if not done in the previous 4 weeks). All patients' files and radiologic images (in Digital Imaging and Communications in Medicine [DICOM] format) must be available for source verification and for central review.

Assessment of response will be made using the RANO criteria ([Appendix 2](#)). Responses should be confirmed with two assessments at least 4 weeks apart. Efficacy evaluations using the RANO criteria involve post-contrast MRI findings, non-contrast T1 and T2 FLAIR images, use of corticosteroid dose, and clinical status per RANO ([Ellingson et al 2015](#)).

Following initial evidence of radiographic progressions and due to the potential for pseudo-progression patients may, at the discretion of the investigator, remain on treatment until further imaging is performed 4 to 8 weeks (at the discretion of the investigator) after the initial determination of potential progression.

8.3.2. Central Independent Radiology Facility (IRF)

An IRF may evaluate imaging studies and supportive clinical data in a central and independent fashion. The IRF will comprise board-certified radiologists who will identify baseline lesions and assign post-baseline time point responses. Details regarding IRF member qualification, training, methods, procedures, and other issues relevant to IRF will be described in the IRF Charter.

The IRF will not perform independent clinical evaluations. The IRF may be asked to evaluate response status and may request select clinical data solely to aid in the interpretation of radiographic images. All scans should be sent to the IRF within 1-3 business days of acquisition (as detailed in the Study Manual).

All radiologic studies acquired at all scheduled time points and any additional (unscheduled) radiologic images acquired to evaluate for potential metastatic disease also must be sent to the IRF.

Minimal standards for imaging platform and machine settings as well as information regarding transfer of scan files to the IRF can be found in the Study Imaging Manual.

Assessment of response will be made using the RANO criteria as outlined in [Appendix 2](#).

8.4. Safety

8.4.1. Adverse Events

Safety assessments should be performed at the study center visits throughout the study. See [Appendix 1](#) for the schedule of assessments and windows for assessments.

All AEs and SAEs, regardless of the relationship to study treatment, will be collected per the process and for the time periods outlined in [Section 10](#). The accepted regulatory definition of AEs, SAEs, and important additional requirements for SAE reporting are outlined in [Section 10](#).

8.4.2. Physical Examination, Vital Signs, ECOG Performance Status, Weight and Height

A complete or limited physical examination, vital signs (systolic and diastolic blood pressure, pulse rate and oral, temporal or tympanic temperature), weight, height and ECOG performance status will be performed at time points specified in [Appendix 1](#).

A complete physical examination should include an evaluation of head, eyes, ears, nose and throat, neck, heart, chest (including lungs), abdomen, extremities, skin, lymph nodes, cardiovascular status and neurological status. A limited physical examination should include neurological status and additionally be directed at the evaluation of symptoms or specific safety issues. Changes from baseline abnormalities should be recorded at each subsequent physical examination. New or worsened abnormalities should be recorded as AEs if appropriate.

ECOG performance status will be determined as outlined in [Appendix 3](#).

8.4.3. Electrocardiograms

Single 12-lead ECGs with assessment of PR interval, QRS duration, and QTc interval will be obtained as outlined in [Appendix 1](#). Additional ECGs will be performed if clinically indicated. To minimize postural variability, it is important that patients are resting and in a semi-recumbent supine position for ≥ 5 minutes prior to each ECG collection. Blood draws and other procedures should be avoided during the period immediately before ECG measurement, and activity should be controlled as much as possible to minimize variability because of the effects of physiologic stress. Screening ECG must be performed within 14 days of Day 1. For the scheduled ECG assessment at the EOT visit, ECG does not have to be repeated if it was performed within 14 days of the EOT visit.

8.4.4. Laboratory Studies

Samples for hematology, chemistry, and coagulation profiles will be drawn and analyzed locally. All other required blood samples will be sent to a central laboratory for analysis throughout the study.

A detailed description of the procedures for sample collection, handling, storage, and shipment of the laboratory samples and all material such as test tubes and labels is provided in the laboratory manual.

Laboratory studies will be performed at the time points specified in [Appendix 1](#) (including allowed windows of assessment) and may also be performed as medically necessary. Laboratory assessments should be done before study treatment. Screening blood and urine tests must be performed within

14 days of Day 1. If they were performed within 7 days of Day 1, they do not need to be repeated on Day 1.

8.4.4.1. Hematology

Hematology includes hemoglobin, platelet count, white blood cell count, neutrophil count, and lymphocyte count.

8.4.4.2. Chemistry

Chemistry includes albumin, alkaline phosphatase, AST, ALT, blood urea nitrogen, chloride, creatinine, glucose, lactic acid dehydrogenase, phosphate, potassium, sodium, total bilirubin, and total protein.

8.4.4.3. Coagulation

The coagulation profile includes INR and aPTT.

8.4.4.4. Urinalysis with Dipstick

Urinalysis will be assessed using urine dipstick. Urine microscopy will be performed if urine dipstick is abnormal. Urinalysis includes blood, protein, ketones, glucose, red blood cells, and white blood cells.

8.4.4.5. Hepatitis B Serology Test

Testing for hepatitis B will be performed by the local laboratory at Screening and will include HBV serology (HBsAg, HBsAb and HBcAb) and viral load assessment (HBV DNA).

8.4.4.6. Pregnancy Testing

The Clinical Trials Facilitation Group's recommendations related to contraception and pregnancy testing in clinical trials include for females with childbearing potential the use of highly effective forms of birth control ([Appendix 4](#)) and testing for pregnancy every 28 days. For women of childbearing potential, a screening serum pregnancy test must be obtained within 7 days prior of Day 1. For subsequent pregnancy testing on study and at end of treatment, urine pregnancy tests are allowed. If a urine pregnancy test is positive, a confirmatory serum pregnancy test is required.

8.5. Pharmacokinetics

Pharmacokinetic samples will be collected from patients in all cohorts at the following time points ([Appendix 1](#)): predose (within 30 min prior to dose) and 2 hours (\pm 30 min) post-dose on both Day 1 and Day 15 (collection takes place in Cycle 1 for Arm C). If pamiparib treatment is administered only for a 2-week (14-day) time period, PK samples will be collected on Day 1 and Day 14 instead. The time of study drug administration on the day prior to Day 15 (Day 14 for patients receiving only 2 weeks of pamiparib) must be recorded on the eCRF. Details concerning collection, handling, and processing of the PK plasma samples will be provided in the laboratory manual.

8.6. Biomarkers

Patients are required to provide archival tumor tissues for the analysis of candidate predictive biomarkers. This is optional and dependent upon tissue availability in the dose escalation phase but mandatory in the dose expansion phase. Archival tumor tissue, either a formalin-fixed paraffin-embedded block with tumor tissue (preferred) or, ideally, around 15 unstained slides will be sent to the central laboratory for biomarker testing.

Candidate markers will include, but are not limited to:

1. Markers of disease (eg, DNA hypermethylation, PTEN loss or mutational status, EGFR/EGFRviii)
2. Markers related to response or resistance to TMZ (eg, *MGMT* levels and methylation status, APNG, gH2Ax)
3. Markers related to response or resistance to PARP inhibitors (eg, HRD, *BRCA* loss or mutational status, ATM, MRE11, RAD51)

Patients will also provide blood samples to be processed into serum, plasma and cell fractions for the analysis of germline mutations, such as, but not limited to, *BRCA*, and circulating markers, such as, but not limited to, circulating tumor cells (CTCs) and circulating nucleic acids [CNAs].

Instructions for the processing, storage, and shipping of samples will be provided in the laboratory manual.

8.7. Appropriateness of Measurements

All safety and PK assessments used in this study are standard, and generally recognized as reliable, accurate, and relevant.

9. DATA HANDLING AND QUALITY ASSURANCE

This study will be organized, performed, and reported in compliance with the protocol, standard operating procedures (SOPs), working practice documents, and applicable regulations and guidelines. Study center audits may be made periodically by the sponsor's or the contract research organization's qualified compliance auditing team, which is an independent function from the study team responsible for conduct of the study.

9.1. Data Collection

Data will be entered into the eCRFs in an electronic data capture (EDC) system.

Data collection on the eCRF must follow the instructions described in the eCRF Completion Guidelines. The investigator has ultimate responsibility for the collection and reporting of all clinical data entered on the eCRF. The investigator or designee must sign the completed casebooks to attest to its accuracy, authenticity, and completeness.

Data contained in the eCRFs are the sole property of BeiGene and should not be made available in any form to third parties without written permission from BeiGene, except for authorized representatives of BeiGene or appropriate regulatory authorities.

9.2. Data Management/Coding

All final patient data, both eCRF and external data (eg, laboratory data), collected according to the protocol, will be stored at BeiGene at the end of the study.

Standard procedures (including following data review guidelines, computerized validation to produce queries, and maintenance of an audit file, which includes all database modifications) will be followed to support accurate data collection. Data will be reviewed for outliers, logic, data inconsistencies, and completeness.

During the course of the study, a study monitor will make study center visits to review protocol compliance, compare eCRFs against individual patient's medical records, and ensure that the study is being conducted according to pertinent regulatory requirements.

eCRF entries will be verified with source documentation. The review of medical records will be performed in a manner to ensure that patient confidentiality is maintained. Checking the eCRFs for completeness, clarity, and cross checking with source documents is required to monitor the progress of the study. Direct access to source data is also required for inspections and audits, and will be carried out giving due consideration to data protection and medical confidentiality.

Adverse events will be coded using the Medical Dictionary for Regulatory Activities (MedDRA[®]) Version 18.1 or higher. Concomitant medications will be coded using the World Health Organization Drug Dictionary. Concomitant diseases/medical history will be coded using the MedDRA Version 18.1 or higher.

9.3. Quality Assurance

To ensure compliance with GCP and all applicable regulatory requirements, the sponsor may conduct a quality assurance audit. Regulatory agencies may also conduct a regulatory inspection of this study. Such audits/inspections can occur at any time during or after completion of the study. If an audit or inspection occurs, the investigator and institution agree to allow the auditor/inspector direct access to all relevant documents and to allocate his/her time and the time of his/her personnel to the auditor/inspector to discuss findings and any relevant issues.

10. SAFETY MONITORING AND REPORTING

The investigator is responsible for the monitoring and documentation of events that meet the criteria and definition of an AE or SAE as provided in this protocol.

10.1. Adverse Events

10.1.1. Definition and Reporting of an Adverse Event

An AE is defined as any unfavorable and unintended sign (including an abnormal laboratory finding), symptom, or disease (new or exacerbated) temporally associated with the use of a study drug, whether considered related to study drug or not.

Examples of an AE include:

- Worsening of a chronic or intermittent pre-existing condition including an increase in severity, frequency, duration, and/or has an association with a significantly worse outcome.
- New conditions detected or diagnosed after study drug administration even though it may have been present before the start of the study.
- Signs, symptoms, or the clinical sequelae of a suspected interaction.
- Signs, symptoms, or the clinical sequelae of a suspected overdose of either study drug or a concurrent medication (overdose per se should not be reported as an AE or SAE).

When an AE or SAE occurs, it is the responsibility of the investigator to review all documentation (eg, hospital progress notes, laboratory results and diagnostics reports) relative to the AE or SAE. The investigator will then record all relevant information regarding an AE or SAE in the eCRF. However, there may be instances when copies of medical records for certain cases are requested by the sponsor. In this instance, all patient identifiers will be blinded on the copies of the medical records before submission to the sponsor.

10.1.2. Assessment of Severity

The investigator will make an assessment of severity for each AE and SAE reported during the study. AEs and SAEs should be assessed and graded based upon the NCI-CTCAE Version 4.03 or higher.

Toxicities that are not specified in the NCI-CTCAE will be defined as follows:

- Grade 1: Mild; asymptomatic or mild symptoms; clinical or diagnostic observations only; intervention not indicated
- Grade 2: Moderate; minimal, local or noninvasive intervention indicated; limiting age-appropriate instrumental activities of daily living
- Grade 3: Severe or medically significant but not immediately life-threatening; hospitalization or prolongation of hospitalization indicated; disabling; limiting self-care activities of daily living

- Grade 4: Life-threatening consequences; urgent intervention indicated
- Grade 5: Death related to AE

NOTE: The terms “severe” and “serious” are not synonymous. Severity is a measure of intensity (eg, grade of a specific AE, mild [Grade 1], moderate [Grade 2], severe [Grade 3], or life-threatening [Grade 4]); whereas seriousness is classified by the criteria based on the regulatory definitions. Seriousness serves as the guide for defining regulatory reporting obligations from the sponsor to applicable regulatory authorities as described in [Section 10.2](#).

10.1.3. Assessment of Causality

The investigator is obligated to assess the relationship between the study drug and the occurrence of each AE or SAE. The investigator will use clinical judgement to determine the relationship. Alternative causes, such as natural history of the underlying diseases, concomitant therapy, and other risk factors, and the temporal relationship of the AE or SAE to the study drug will be considered and investigated. The investigator will also consult the IB and/or Product Information, for marketed products, in the determination of his/her assessment.

There may be situations when an SAE has occurred, and the investigator has minimal information to include in the initial report to the sponsor. However, it is very important that the investigator always provides assessment of causality for every SAE before transmission of the SAE report/eCRF to the sponsor since the causality assessment is one of the criteria used when determining regulatory reporting requirements. The investigator may change his/her opinion of causality in light of follow-up information, amending the SAE report/eCRF accordingly.

The causality of each AE should be assessed and classified by the investigator as “related” or “not related.” An AE is considered related if there is at least “a reasonable possibility” that the AE may have been caused by the study drug (ie, there are facts, evidence, or arguments to suggest possible causation, *or a causal relationship between the AE and the drug cannot be ruled out*). A number of factors should be considered in making this assessment, including:

- Temporal relationship of the AE to the administration of study treatment/study procedure
- Whether an alternative etiology has been identified
- Mechanism of action of the study drug
- Biological plausibility

An AE should be considered “related” to study drug if any of the following are met, otherwise the event should be assessed as not related:

- There is clear evidence to suggest a causal relationship, and other possible contributing factors can be ruled out.
- There is evidence to suggest a causal relationship, and the influence of other factors is unlikely.

- There is some evidence to suggest a causal relationship (eg, the AE occurred within a reasonable time after administration of the study drug). However, the influence of other factors may have contributed to the AE (eg, the patient's clinical condition or other concomitant AEs).

10.1.4. Follow-Up of Adverse Events

When treatment is interrupted or permanently discontinued due to an AE or abnormal laboratory value the patient must be followed at a frequency as medically indicated until resolution or stabilization of the event, whichever comes first.

All patients will be followed for AEs and SAEs for at least 30 days following the last dose of pamiparib or initiation of new anticancer therapy, whichever occurs first. For prolonged hematological toxicities, treatment should be interrupted and blood counts should be monitored weekly until recovery.

If the levels have not recovered to CTCAE Grade ≤ 1 or baseline after 4 weeks, the patient should be referred to a hematologist for further investigations, including bone marrow analysis and blood sample for cytogenetics. If myelodysplastic syndrome/acute myeloid leukemia is diagnosed, the event should be reported as an SAE regardless of causality.

All AEs and SAEs documented at a previous visit/contact and designated as ongoing will be reviewed at subsequent visits/contacts.

All AEs and SAEs will be followed until resolution, the condition stabilizes or is considered chronic, the AE or SAE is otherwise explained, the patient is lost to follow-up or the patient withdraws consent. Once resolved, the appropriate AE eCRF page(s) will be updated. The investigator will ensure that follow-up includes any supplemental investigations as may be indicated to elucidate the nature and/or causality of the AE or SAE. This may include additional laboratory tests or investigations, histopathological examinations, or consultation with other health care professionals.

The sponsor may request that the investigator perform or arrange for the conduct of supplemental measurements and/or evaluations to elucidate as fully as possible the nature and/or causality of the AE or SAE. The investigator is obligated to assist. If a patient dies during participation in the study or during a recognized follow-up period, the sponsor will be provided with a copy of any postmortem findings, including histopathology.

New or updated information will be recorded on the originally completed SAE report, with all changes signed and dated by the investigator. The updated SAE report should be resent to the sponsor within the time frames outlined in [Section 10.5.1](#).

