10.3. Timing, Frequency, and Method of Capturing Adverse Events and Serious Adverse Events

10.3.1. Adverse Event Reporting Period

After the ICF has been signed but before study treatment, only SAEs should be reported, as required per [Section 10.5](#).

After initiation of study treatment, all AEs and SAEs, regardless of relationship to study treatment, will be reported until 30 days after the last study treatment or initiation of new anticancer therapy, whichever occurs first. After this period, the investigator should report any SAEs that are believed to be related to prior study treatment.

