10.7. Poststudy Adverse Events

A poststudy AE or SAE is defined as any AE that occurs outside of the AE/SAE reporting period, as defined in [Section 10.3.1](#).

Investigators are not obligated to actively seek AEs or SAEs in former patients. However, if the investigator learns of any SAE, including a death, at any time after a patient has been discharged from the study, and he/she considers the SAE related to the study drug, the investigator will notify the sponsor.

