6.5.3 Adverse Events

The AE verbatim descriptions (investigator terms from the eCRF) will be classified into standardized medical terminology using Medical Dictionary for Regulatory Activities (MedDRA). Adverse events will be coded to MedDRA (Version 22.0 or higher), lower level term closest to the verbatim term. The linked MedDRA preferred term (PT) and primary system organ class (SOC) are also captured in the database.

A treatment-emergent adverse event (TEAE) is defined as an AE that had an onset date on or after first dose of study treatment or was worsening in severity from baseline (pretreatment) up to 30 days following permanent study treatment discontinuation or initiation of new anti-cancer therapy, whichever occurs first. All AEs, treatment emergent or otherwise, will be presented in patient data listings. TEAEs will be summarized and presented for all cohorts and all arms.

An overview table, including the number and percentage of patients with any TEAEs, any treatment-related TEAEs, treatment-emergent serious adverse events (SAEs), TEAEs with grade 3 or above, treatment-related SAEs, TEAEs that led to death, and TEAEs that led to treatment discontinuation, dose reduction or dose interruption will be provided. Treatment-related AEs include those events considered by the investigator to be unlikely, possibly or probably or definitely related to study drug or with missing assessment of the causal relationship. The overview table will be completed for each study Arm.

The following TEAEs will also be tabulated in summary tables for all arms and cohorts:

- TEAE
- SAE
- TEAEs with grade 3 or above
- Treatment-related TEAEs
- Treatment-related SAEs
- TEAEs that led to death
- TEAEs leads to treatment discontinuation
- TEAEs leads to dose reduction or dose interruption of either Pamiparib or RT or TMZ

A patient will be counted only once by the highest severity grade according to CTCAE v.4.03 within an SOC and PT, even if the patient experienced more than 1 TEAE within a specific SOC and PT. TEAEs with grade 3 or above will also be summarized by PT in descending order.

In addition, the following listings will be provided:

- Listing of all AEs,
- Listing of all SAEs
- Treatment-related AEs
- Grade 3 or above AEs
- AEs leading to death
- AEs leading to treatment discontinuation

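### Reporting instructions for late MDS/AML conflict between Protocol 10.1.4 and 10.3.1/10.7, and a reported case with onset after the 30-day window would enter no SAP summary table

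*Protocol*

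**What the plan says.** Protocol 10.1.4 deals with prolonged hematological toxicity. Treatment is interrupted and counts are checked weekly. If they have not returned to Grade 1 or less "or baseline after 4 weeks, the patient should be referred to a hematologist for further investigations", including marrow and cytogenetics. The next sentence is the special rule: "If myelodysplastic syndrome/acute myeloid leukemia is diagnosed, the event should be reported as an SAE regardless of causality". It carries no time limit.

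The general reporting rules differ. Under Protocol 10.3.1, all AEs and SAEs "will be reported until 30 days after the last study treatment or initiation of new anticancer therapy, whichever occurs first", and then: "After this period, the investigator should report any SAEs that are believed to be related to prior study treatment". Protocol 10.7 adds: "Investigators are not obligated to actively seek AEs or SAEs in former patients". If an investigator does learn of a post-study SAE, the condition is that "he/she considers the SAE related to the study drug, the investigator will notify the sponsor". The adverse-event footnotes in Appendix 1 (Table 1 note o, Table 2 note p, Table 3 note o, Table 4 note m) repeat the 10.3.1 rule. None of these places mentions MDS/AML.

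SAP 6.5.3 defines a treatment-emergent event by onset or worsening "up to 30 days following permanent study treatment discontinuation or initiation of new anti-cancer therapy", whichever is first. Its summary tables, including the SAE table, stand under a heading that restricts them to treatment-emergent events. Listings of all AEs, treatment-emergent or not, and of all SAEs are also planned. There is no separate MDS/AML or second-malignancy summary.

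**The concern.** MDS/AML is the one late harm for which the protocol sets its own work-up and removes the causality judgement. The general sections bring that judgement back once the window closes, and do not say which rule applies. The referral pathway itself takes 4 weeks, so it can deliver a diagnosis at or after the edge of a 30-day window.

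Two things are at stake. One is consistent reporting: two sites with the same late case could act differently, and each could cite the protocol. The other is what the safety results show: a late-onset case that is reported correctly still adds nothing to any count.

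The harm is relevant on the protocol's own evidence. Section 1.3.4.1 describes pamiparib as clastogenic in vitro and in vivo, with bone marrow inhibition among its main toxicities. Section 1.2.4 calls marrow toxicity the dose-limiting factor of chemotherapy in glioblastoma. Arms B and C, and maintenance in Arms A and B, combine pamiparib with temozolomide.

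**Working it through.** The plan gives no figure to reproduce. The check sets the rules side by side and then counts days.

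**Step 1: which rule reaches a case with onset after the window?**

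| Source | Judged related | Judged unrelated |
|---|---|---|
| Protocol 10.1.4 | report | report |
| Protocol 10.3.1 and schedule footnotes | report | not asked for |
| Protocol 10.7 | notify if learned of | not asked for |
| SAP 6.5.3 summary tables | not counted | not counted |
| SAP 6.5.3 listings | shown if reported | shown if reported |

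The reporting conflict is confined to the unrelated column. The tabulation gap covers both columns.

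**Step 2: which clock applies?** Three anchors are in use:
- Protocol 10.1.4: "All patients will be followed for AEs and SAEs for at least 30 days following the last dose of pamiparib", so the last pamiparib dose.
- Protocol 10.3.1: the last study treatment. Section 11.2.1 counts radiotherapy (RT) as study treatment.
- SAP 6.5.3: permanent discontinuation of study treatment.

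**Step 3: day counts.** Inputs are the 4-week non-recovery period (4 × 7 = 28 days) and the 30-day window. I assume the 4 weeks run from the interruption of dosing, taken as day 0 unless stated. Overlap is window close minus referral day.

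| Situation | Referral | Window closes | Overlap |
|---|---|---|---|
| All study treatment stops on day 0; 10.3.1 clock | day 28 | day 30 | 30 − 28 = 2 days |
| Last dose on day 0, non-recovery starts d days later; 10.3.1 clock | day 28 + d | day 30 | 2 − d days; referral is past day 30 once d exceeds 2 |
| Pamiparib/TMZ held on day 0, RT continues r more days; 10.3.1 clock | day 28 | day r + 30 | r + 2 days (r = 14 gives 16) |
| Drugs held on day 0, discontinuation dated day 28; SAP clock | day 28 | 28 + 30 = day 58 | 58 − 28 = 30 days |

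New anticancer therapy before referral closes the 10.3.1 and SAP windows and removes the overlap in every row. In the last row, if no RT is being given, the 10.3.1 window still closes on day 30. The two windows for the same patient then differ by 58 − 30 = 28 days.

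**Step 4: onset or diagnosis?** Treatment-emergent status turns on the onset date, not the date of diagnosis. A case whose onset is dated back to an in-window cytopenia would be tabulated even if the marrow result came later. A case entered with a later onset date would not. Neither document says how to date it.

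**The case against.** The best defence is that the referral-pathway case is already covered. The MDS/AML sentence directly follows the referral sentence, with no time limit and no causality condition, and a specific rule can be read as prevailing over general ones. Sections 10.3.1 and 10.7 do not forbid reporting an unrelated SAE. Section 10.1.4 also requires known events to be followed until they resolve, stabilise or are otherwise explained, so an in-window cytopenia later shown to be MDS/AML is follow-up of a recorded event. This stands, and it limits the first problem to unreconciled instructions. It is not a missing duty.

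A reader might infer that late cases would vanish from the results. The documents do not support that: SAP 6.5.3 lists all AEs and all SAEs whatever their treatment-emergent status. With 116 patients, a listing line would be visible to a careful reader. It is still not a count or a rate by arm.

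The protocol's meaning of related is wide, since it includes events where a causal link cannot be excluded (10.1.3). Few late cases should therefore be called unrelated. But the same section asks investigators to weigh concomitant therapy and alternative causes. Arm C expansion patients have already had RT with temozolomide (inclusion criterion 19), and 7.1.4.3 names radiation-induced neoplasms, so other explanations will be at hand.

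The Long-Term Follow-up columns for Arms A, B and C do mark adverse events, but the attached footnotes carry the related-only rule. Short survival also limits late cases: Protocol Table 1 gives median OS of 2.6 to 13.7 months in newly diagnosed unmethylated disease.

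**Conclusion.** The point holds as two limited defects.

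- **Conflict.** For MDS/AML arising after the window and judged unrelated, 10.1.4 requires a report, while 10.3.1, 10.7 and four schedule footnotes do not ask for one. A case is lost entirely only if a site follows the general sections over 10.1.4.
- **Tabulation.** A reported case with onset after the SAP window enters no summary table, whatever its causality. Read as written, the tables would show zero for that case. This takes the SAE table as limited to treatment-emergent events, as its heading says.

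The 2-day overlap applies only when counts fail to recover after the last dose of all study treatment. A reader might take it as general, but continuing RT or a later discontinuation date lengthens it, to 30 days in the day-58 example. A reader might also want a probability that a case is missed. The documents give no incidence of MDS/AML, no share with late onset and no share judged unrelated, so no such figure can be supported. The effect is on the completeness of the safety summary. No efficacy result is touched.

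**What to change.** **Protocol.** Reconcile 10.1.4, 10.3.1, 10.7 and the four schedule footnotes so that the MDS/AML reporting rule, including its time frame and whether relatedness matters, reads the same everywhere. Align the window anchors (last pamiparib dose, last study treatment, permanent discontinuation), or state why they differ.

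**SAP 6.5.3.** Add one table of all reported MDS/AML cases at any time after first dose, by arm, in the Safety Analysis Set, whatever the treatment-emergent status or causality. Show time from first and last dose and any subsequent anticancer therapy. State how onset is dated when a cytopenia is later diagnosed as MDS/AML.

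**Cost.** A few sentences of protocol text and one small table, built from SAE reports that 10.1.4 already requires. No dose or treatment rule changes. Some late cases may reflect later therapy, which is why that therapy should be shown beside them. The 12-weekly survival contact (6.6.3) now collects survival and further anticancer therapy only, so asking about MDS/AML there would add a small data item. The table does not depend on that addition.
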